5.4 Supportive measures during treatment

Supportive care measures will be according to institutional and Leukemia Department guidelines.

5.5 Management of toxicities and dose modifications

5.5.1 At all cycles

All dose delays, reductions, and modifications for hematologic and non-hematologic toxicities will be assessed according to Sections 5.5.2 and 5.5.3.

5.5.2 Hematologic (blood/bone marrow) toxicity

No dose reductions, delays, or modifications are required for hematologic toxicities during the first cycle. It is assumed that low counts at diagnosis are due to involvement by the disease process and require therapy for improvement. Likewise, patients with persistent disease who are considered for more therapy can be expected not to have a recovery of their hematologic parameter and thus, no dose reductions, delays, or modifications are required for hematologic toxicities unless it is considered to do so in the best interest of the patient and after discussion with the Principal investigator.

5.5.3 Non-hematologic toxicity

If grade 2 toxicity occurs during any course of therapy, and it is unresponsive to optimal treatment and is possibly related to OM treatment, OM treatment may be withheld after the onset of an event until the AE has returned to baseline or \leq grade 1. If the AE has returned to baseline or \leq grade 1 within the 3 days of the first course or subsequent cycles, treatment may resume at the same dose, but missed doses will not be made up.

If grade 3 or greater toxicity occurs during any course of therapy, and it is unresponsive to optimal treatment and is possibly related to OM treatment, OM treatment may be withheld after the onset of an event until the AE has returned to baseline or \leq grade 1. If the AE has returned to baseline or \leq grade 1 within the 3 days of the first course or subsequent courses, treatment may resume but at a reduced OM subcutaneous dose of 1.0 mg/m² twice daily for the remainder of that cycle only. Missed doses will not be made up. In subsequent cycles of therapy, the dose of OM will be the original dose, but the number of consecutive days of OM treatments should then be reduced by 1 day for all subsequent treatment cycles.

If persistent grade 2 toxicity occurs after completion of a cycle of therapy (i.e., after day 3 of each course), and it is unresponsive to optimal treatment and is possibly related to OM treatment, OM treatment may be delayed up to 21 days after the onset of an event or until the AE has returned to baseline or \leq grade 1. Then administer 100% of the planned dose. If toxicity persists longer than 21 days or recurs, the dose may be delayed and the number of consecutive days of OM treatments should then be reduced by 1 day for all subsequent treatment cycles.

If grade ≥ 3 toxicity occurs after completion of the OM treatment (i.e., after day 3 of each course) and it is suspected that OM played a role in toxicity, the next scheduled cycle of OM therapy should be withheld until toxicity returns to grade 0 or 1 or to baseline. The dose of OM will then remain the same, but the treatments may then be reduced by 1 day for all subsequent treatment cycles. Additional repeat dose reduction of 1 day will be made if toxicity recurs or persists. The number of consecutive days of OM may be reduced and the intervals between cycles may be shortened or increased, if clinically indicated. Missed doses of OM will not be made up.

Dose modifications different from those stated in the protocol will be decided jointly by the principal investigator and the treating physician.

Adverse events which are moderate to severe in intensity and which are assessed as possibly or probably related to study drug, may result in the termination of study treatment in the affected study patient.

Such termination should be reviewed with the principal investigator at the earliest possible time. Following review with the principal investigator, the study patient may be permanently withdrawn from the study depending upon the nature and severity of the event.

5.6 Supportive care

Supportive care measures including blood products, infection prophylaxis and growth factors will be administered according to institutional and Leukemia Department guidelines.

6.0 Pretreatment Evaluation

History and physical (including weight and blood pressure), CBC with differential and platelets, chemistry profile (total bilirubin, serum creatinine, SGPT or SGOT, uric acid, LDH, potassium, magnesium, glucose), and an ECG within 14 days of therapy start.

Serum or urine HCG at screening for women of childbearing potential and within 3 days prior to treatment start.

Bone marrow aspirate and/or biopsy within 28 days of therapy start. The bone marrow evaluation will include immunophenotyping by flow cytometry and cytogenetic studies.

MDS flow panel

7.0 Evaluation During Study

Patient will have physical examination prior to each course. In addition:

1. CBC with differential and platelet counts at least once a week until remission, then every 2 to 4 weeks during active treatment, and every 4 to 8 weeks thereafter as long as on study. No differential is needed if the WBC is $< 1.0 \times 10^9/L$.
2. Creatinine, bilirubin, ALT or AST once monthly.

3. Marrow aspirate to confirm response, to be performed after cycle 2 then every 2 to 4 cycles until response observed, then as clinically indicated
4. If pre-treatment MDS Flow Panel was initially abnormal, sequential MDS Flow Panel to be performed after cycle 2 then every 2 to 4 cycles until response observed, then as clinically indicated if possible.
5. Conventional cytogenetics to be performed after cycle 2 then every 2 to 4 cycles until response observed, then as clinically indicated.

The patient may have the laboratory work done by their home physician and the results reported to the research nurse for the study.

Patient will be followed for survival at MDACC every 3 to 6 months for up to 5 years after completion of active treatment and while still on study. If the patient is unable to return to MD Anderson Cancer Center the follow-up visits may be conducted via telephone.

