5.2 General study treatment plan

The intent of the study design is for all patients to receive up to 12 courses. Treatment will be continued during the duration of the study unless patients exhibit evidence of treatment failure, disease progression, experience an unacceptable toxicity, or the investigator determines that discontinuation of treatment is in the best interest of the patient.

Patients will be treated with study drugs based on a calculation determined from the patient's body surface area (BSA). BSA will be calculated before each cycle and will be based on the patient's height (measured at baseline) and weight (measured each cycle) and will be adjusted downward to "ideal" weight.

"Patients will be instructed to self-administer OM at home and return unused intact drug syringes to be disposed of by the study staff or dropped off to the Investigational Pharmacy. Patients will be given a Research Medication Diary to record the medication taken each day. Patients will be instructed to bring the diary and any unused intact medication syringes with them to all study visits. Any unused drug will be disposed of per institutional standard practice.

5.3 Dose modifications:

Patients will receive their OM treatment every 4-7 weeks:

- a. OM 1.25 mg/m² SQ every 12 hours (+/- 3 hours) for 3 days.

Courses will be repeated every 4-7 weeks. Subsequent courses can be given with modified schedules as detailed below:

- a. Stable or improved MDS with grade 2 or less toxicity: use same dose schedule as previous course.
- b. MDS not improved with grade 2 or less toxicity, increase dose schedule to 4 days of OM if needed.
- c. MDS stable/improved or not improved with grade 3-4 toxicity, give subsequent course with 2 days of OM if clinically indicated; otherwise may take patient off study.
- d. Other modifications in the dose schedule based on response and toxicity of individual patient are allowed if in the patient best interest, after discussion with principal investigator.
- e. Missed doses will not be made up.

In addition, any drug-related, non-hematologic toxicity experienced by a patient should return to \leq grade 2 or the baseline grade before the patient continues treatment.

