9.0 Criteria for Removal from the Study

Patients are free to withdraw consent and discontinue participation in the study at any time and without prejudice to further treatment. Patients may be discontinued from the study for the following reasons:

1. Patient requests discontinuation.
2. There is unacceptable toxicity (i.e., NCI CTCAE version 4 grade 4 drug-related non hematologic toxicity).
3. Patient experiences an NCI CTCAE version 4 \geq grade 3 drug-related non-hematologic toxicity or clinically significant infection of any grade that is not recovered by Day 75 from the onset of the toxicity.
4. Patient experiences a third occurrence of an NCI CTCAE version 4 grade 3 drug-related non-hematologic toxicity.
5. Patient experiences asymptomatic grade 2 total bilirubin or creatinine abnormality that is not recovered by Day 75 from the onset of the toxicity.
6. There is a need for any treatment not allowed by the protocol.
7. Treatment failure or disease relapse.
8. Investigator discretion.

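### The only survival follow-up rule (section 7.0) is qualified by an undefined on-study condition, so it is unclear whether deaths after removal from the study are collected for the primary OS endpoint

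*Combined protocol and SAP*

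**What the plan says.** Section 7.0 contains the only survival follow-up rule in the available text. Contact is every 3 to 6 months, "for up to 5 years after completion of active treatment and while still on study". For patients who cannot return, "the follow-up visits may be conducted via telephone". Item 1 of the same section uses the same idea as a limit: blood counts continue "every 4 to 8 weeks thereafter as long as on study".

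Leaving the study is described in three places:

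- Section 9.0: "Patients may be discontinued from the study for the following reasons". The list includes unacceptable toxicity, need for a treatment the protocol does not allow, and "Treatment failure or disease relapse".
- Section 5.3, on grade 3-4 toxicity: "otherwise may take patient off study".
- Section 5.5.3 (closing paragraphs): "the study patient may be permanently withdrawn from the study depending upon the nature and severity of the event".

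Section 5.2 names overlapping events as reasons to stop treatment: "Treatment will be continued during the duration of the study unless patients exhibit evidence of treatment failure, disease progression".

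Section 8.7 defines OS as time from treatment start to death from any cause. Section 11.0 makes OS primary, plans 12 months of follow-up after the last accrual, and claims 84% power with 80 patients for a median of 6 against 4.2 months. It mentions no allowance for loss to follow-up. Section 11.3 names Kaplan-Meier and does not mention removed patients.

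**The concern.** The plan does not keep leaving treatment apart from leaving the study. Failure and unacceptable toxicity are reasons to stop treatment in 5.2 and reasons for removal from the study in 9.0. If survival follow-up lasts only while a patient is on study, a patient removed for relapse in month 3 who dies in month 5 would be censored in month 3.

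These removals are foreseeable: section 2.1 puts median survival after hypomethylating failure below 5 months. OS is compared with a fixed historical median, so no control arm would share the same loss of deaths. The same follow-up data feed the OS futility rule in 11.1. The documents do not tell staff which reading to apply.

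**Working it through.** **1. The plan's own figure.** Inputs from section 11.0: N = 80, medians 4.2 and 6 months, exponential survival, two-sided 0.05, accrual 1-5 per month, 12 further months. The test is not named; a one-sample test on the log-hazard scale is assumed here.

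Deaths needed for 84% power: ((1.96 + 0.994)/ln(6/4.2))² = (2.954/0.3567)² ≈ 69.

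Deaths expected with full follow-up, with λ = ln2/6, F = 12 and A = 80/rate: d = 80 × [1 − (e^(−λF) − e^(−λ(A+F)))/(λA)].

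- 5 per month (A = 16): d = 70.9; power = Φ(√70.9 × 0.3567 − 1.96) = 85.2%.
- 3 per month (A = 26.7; Table 1 implies about this rate, e.g. 66 patients in 34.0 − 12 = 22 months): d = 73.8; power 86.5%.

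On this scale 84% needs about 69 deaths against 71-74 expected, a margin of two to five deaths. On the hazard-rate scale, full follow-up gives 81.8% to 84.2% across accrual rates of 5 to 1 per month. Some other test forms leave more slack (about 89% on the median scale at 3 per month), so 69 is a back-calculation and not a number in the plan.

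**2. Model A: removal unrelated to prognosis.** Assumed: median time to removal m = 2-4 months, accrual 3-5 per month, true median 6 months, and a share p of removed patients censored at removal. With μ = ln2/m, deaths if all are censored at removal are:

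d_c = 80 × λ/(λ+μ) × [1 − (e^(−(λ+μ)F) − e^(−(λ+μ)(A+F)))/((λ+μ)A)].

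For m = 2, d_c = 20.0; for m = 4, d_c = 31.8-31.9. Observed deaths are (1 − p) × d + p × d_c. Worst corner at p = 0.50 (5 per month, m = 2): 0.5 × 70.9 + 0.5 × 20.0 = 45.4 deaths, power 67.2%. Best corner (3 per month, m = 4): 52.8 deaths, power 73.7%.

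| Share of removed patients lost | Deaths | Power |
|---|---|---|
| 0 | 71-74 | 85-86% |
| 25% | 58-63 | 78-81% |
| 50% | 45-53 | 67-74% |
| 100% | 20-32 | 35-53% |

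Simulation of the one-sample log-rank test (20,000 trials per cell) gives the same ranges. In this model there is no bias: at a true median of 4.2 months the apparent median stays at 4.2 and false rejection stays at about 2% for every p.

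**3. Model B: removed patients do worse.** Same removal times and accrual, but the death hazard after removal is k = 1.5-2 times the on-study hazard h, with h set so that true survival at 4.2 months is 0.5:

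S(t) = e^(−(h+μ)t) + μ/(μ − (k−1)h) × [e^(−kht) − e^(−(h+μ)t)].

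Example, m = 4, k = 2: h = 0.131 per month. If every removed patient is censored at removal, the apparent median is ln2/0.131 ≈ 5.3 months against a true 4.2.

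| Share lost | False rejection (true median 4.2) | Apparent median (months) |
|---|---|---|
| 0 | 0.03-0.22% | – |
| 25% | 0.2-0.6% | 4.3-4.4 |
| 50% | 1.3-1.7% | 4.4-4.6 |
| 75% | 3.7-8.0% | 4.6-5.0 |
| 100% | 10-37% | 4.8-6.1 |

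The reference is 2.5% in the favourable direction. The p = 0 row lies below it partly because k > 1 makes the hazard rise over time, so the exponential null does not fit.

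With a true 6-month median, power in Model B does not fall steadily with loss: 62-77% with full follow-up, 70-74% at 25% lost, 71-80% at 50%, 74-95% at 100%.

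**The case against.** The strongest reply is that the clause is additive: survival is followed during the study and also for 5 years after treatment. That fits the any-cause definition of OS, the 12 further months and the telephone option. Section 5.3 uses leaving the study almost as a synonym for stopping treatment; in that sense the literal reading would be empty, since nobody is both past treatment and still on it. The phrase may also only mark the limit set by withdrawal of consent, with which section 9.0 opens. Removal under 9.0 is permitted, not required.

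Much of this stands. A reader might infer that the plan contradicts itself or that deaths will be missed; the text shows neither. A reader might also take the training sentence in 11.1 as proof that full death capture was intended, but it asks only for timely data entry and says nothing of removed patients. A missing censoring sentence in 11.3 is weak evidence too, because censoring at the date last known alive is the usual Kaplan-Meier convention.

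What does not fall away is that item 1 of 7.0 uses the on-study phrase as a limit, and that even the additive reading does not say what happens after removal under 9.0. The telephone option changes the means of contact, not its duration.

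**Conclusion.** The point holds as an ambiguity with one harmful reading, on a primary endpoint. The documents give no removal rate, no prognosis after removal and no share of patients who would be lost, so the size is unknown and every figure beyond the reproduced power is conditional on assumptions.

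The harm takes one of two forms. If removal carries no prognosis, power is lost and there is no bias. If removed patients do worse, OS is biased upward, and false rejection passes 2.5% only somewhere between 50% and 75% lost. It would be tempting to add the two, or to call the effect mainly one of power; neither is supported, because they come from different models and power does not fall steadily in the second. The 10-37% false rejection needs every removed patient to be censored at removal, which is the extreme of a reading that is itself in doubt. No effect on the stopping probability in 11.1 was computed and none is claimed.

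The conclusion also rests on the available text: the consent pages and Appendix C (cited as an adverse-event guideline) were not available.

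**What to change.** - Section 7.0: delete the on-study qualifier (the last five words of the quoted follow-up clause). State that every treated patient is followed for survival, by telephone if needed, until death, withdrawal of consent for follow-up, or the analysis cut-off.
- Section 9.0: state that removal from treatment or from the study does not end survival follow-up, so that deaths after removal count as OS events in 11.1 and 11.3.
- Section 11.3 (optional): state that patients not known to have died are censored at the date last known alive.

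The cost is some extra telephone or record checks for patients off treatment. No extra patients or procedures are needed, and no dose or removal criterion changes. If staff already follow everyone, the amendment only records existing practice.

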8.0 Criteria for Response

The response criteria recommended by the MDS International Working Group.

Definitions:

8.1 Complete Response (CR):

Normalization of the peripheral blood and bone marrow with $\leq 5\%$ bone marrow blasts, a peripheral blood granulocyte count $\geq (1.0 \times 10^9/L)$, and a platelet count $\geq 100 \times 10^9/L$.

8.2 Partial response (PR):

As above except for the presence of 6-15% marrow blasts, or 50% reduction if $<15\%$ at start of treatment.

8.3 Hematologic Improvement (HI):

Meets all criteria for CR except for platelet recovery to $\geq 100 \times 10^9/L$.

8.4 Marrow CR:

Blasts $\leq 5\%$ and decrease by $\geq 50\%$ from baseline (baseline blasts should be above 5% to be eligible for marrow CR)

8.5 Clinical benefit:

Platelets increase by 50% and to above $30 \times 10^9/L$ untransfused (if lower than that pretherapy); or granulocytes increase by 100% and to above $1.0 \times 10^9/L$ (if lower than that pretherapy); or hemoglobin increase by 1.5 g/dl ; or transfusion independent; or splenomegaly reduction by $> 50\%$; or monocytosis reduction by $> 50\%$ if pretreatment $> 5 \times 10^9/L$.

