1.0 Objectives

1.1 Primary Objectives:

- a. To assess overall survival and
- b. To assess overall response rate (ORR)

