2.3 Myelodysplastic Syndrome (MDS)

Twenty-eight patients with MDS or MDS evolved into AML were treated with OM 5 mg/m²/daily by continuous intravenous infusion for 9 days.²² Their median age was 67 years. Seven patients achieved CR, and 1 had a PR, for an overall response rate of 28%. Complete response occurred in 3 of 15 patients with MDS and in 4 of 13 patients with MDS that evolved to AML. Median duration of remission was 7 months. In this study group, induction death was high (13 of 28 patients), mainly because of myelosuppression-related infections. Myelosuppression was prolonged and severe, but other toxicities were mild.²² The dose schedule of OM used in this study of elderly patients was effective but toxic. Lower dose schedules of OM may demonstrate similar efficacy and lower toxicity in MDS.

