4.0 Study Design and Eligibility

4.1 Study design

This will be a single arm, single center, open label phase II study assessing OM in patients with intermediate-1 and higher risk MDS post HMA failure. OM will be administered at the dose of 1.25 mg/m² subcutaneously every 12 hours for 3 days. If patient is in the hospital a nurse will administer the treatment. If patient is at home then the treatment can be self-administered or administered by a family member. This Phase II study will include up to a total of 80 patients. The primary endpoint of this Phase II study is achievement of objective response and overall survival. Early stopping rules will be implemented for low CR rates and survival (please refer to section 11.2)

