4.2 Patient eligibility

4.2.1 Inclusion

1. Age >/= 18 years
2. Diagnosis of MDS confirmed within 10 weeks prior to study entry according to WHO criteria. Patients are either not eligible for or choose not to proceed with a stem cell transplant.

3. MDS classified as follows: RAEB-1 (5%-9% BM blasts); RAEB-2 (10%-19% BM Blasts); CMML (5%-19% BM blasts); RAEB-t (20%-29% BM blasts) AND/OR by IPSS: intermediate-1 and high risk patients.
4. No response, progression, or relapse (according to 2006 IWG criteria) following at least 4 cycles of either azactidine or decitabine, which were completed within the last 2 years - AND/OR - intolerance to azacitidine or decitabine defined as drug-related \geq grade 3 hepatic or renal toxicity leading to treatment discontinuation during the preceding 2 years.
5. Eastern Cooperative Oncology Group (ECOG) performance status of \leq 2.
6. Willing to adhere to and comply with all prohibitions and restrictions specified in the protocol.
7. Patient (or patient's legally authorized representative) must have signed an informed consent document indicating that the patient understands the purpose of and procedures required for the study and is willing to participate in the study.)

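### Section 8.2 lets the blast part of partial response be met with little or no fall in marrow blasts

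*Combined protocol and SAP*

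**What the plan says.** Section 8.2 defines PR by reference to CR: "As above except for the presence of 6-15% marrow blasts, or 50% reduction if" the patient had less than 15% blasts at the start of treatment. The CR definition that it carries over (Section 8.1) begins "Normalization of the peripheral blood and bone marrow with" blasts of at most 5%, and requires granulocytes of at least 1.0 and platelets of at least 100 x10^9/L.

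Marrow CR (Section 8.4) is stricter on change. It needs a fall of at least 50% from baseline, and "baseline blasts should be above 5% to be eligible for marrow CR".

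Eligible subtypes (Section 4.2.1) are "RAEB-1 (5%-9% BM blasts); RAEB-2 (10%-19% BM Blasts); CMML (5%-19% BM blasts); RAEB-t (20%-29% BM blasts"; entry by IPSS category is also allowed.

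Section 1.1 lists as a primary objective "To assess overall response rate (ORR"), and Section 4.1 says "The primary endpoint of this Phase II study is achievement of objective response and overall survival". Neither lists the categories that make up response. When Section 2.3 describes an earlier study of the drug, it uses the term for CR plus PR: "Seven patients achieved CR, and 1 had a PR, for an overall response rate of 28" percent.

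**The concern.** The 6-15% limb is an absolute post-treatment range, joined by 'or' to a relative criterion. Nothing in it refers to where the patient started, and no other section adds a minimum fall. The entry criteria admit patients whose blasts already lie in or just above that range, so the blast part of PR can be met without a meaningful blast response. The sentence also supports two readings that classify the same patient differently.

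This matters because response is a primary objective in an open-label, single-arm trial with no control group to absorb a lenient definition. A patient with adequate counts and blasts still at 6-15% fails CR, hematologic improvement and marrow CR, all of which need blasts of 5% or less. Without the loose limb, such a patient could reach only clinical benefit (Section 8.5). If PR counts as response, the same patients also enter response duration and relapse-free survival, which Section 8.6 starts at the date of response.

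**Working it through.** The plan states no figure for PR, so there is none to reproduce. The check is the smallest relative fall that satisfies Section 8.2 at each whole-number baseline.

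**Inputs.** Blast range and 50% clause: Section 8.2. Baselines of 5% to 29%: subtypes in Section 4.2.1. A 5% baseline is left out because it is already at the CR blast level.

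**Readings.**
- Literal: blasts of 6-15% after treatment qualify at any baseline; a 50% fall also qualifies if baseline is below 15%.
- Restrictive: the 6-15% range applies only if baseline is 15% or more; below 15% a 50% fall is required.

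**Formula.** Minimum fall = (baseline - highest qualifying value) / baseline.

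| Baseline | Literal | Restrictive |
|---|---|---|
| 6-14% | 0% | at least 50% |
| 15% | 0% | 0% |
| 16% | 1/16 = 6.3% | 6.3% |
| 17% | 2/17 = 11.8% | 11.8% |
| 18% | 3/18 = 16.7% | 16.7% |
| 19% | 4/19 = 21.1% | 21.1% |
| 20% | 5/20 = 25.0% | 25.0% |
| 29% | 14/29 = 48.3% | 48.3% |

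On the literal reading even a rise, such as 8% to 15%, qualifies. On neither reading does any baseline from 15% to 29% require a 50% fall.

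**Which reading is more natural.** On the literal reading the 50% clause does almost nothing. Halving 12-14% gives 6-7%, already inside the range. Halving 10% or less gives 5% or less, already the CR blast level. The clause has real work only if it divides patients at a baseline of 15%, so the restrictive reading is preferred. The text does not say so.

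**Counting error near 15%.** The documents give no cell count; I assume 200 to 500 cells and binomial counting. If the true percentage stays at 16%, a repeat count reads 15% or less with probability 0.394 (at most 30 of 200) to 0.295 (at most 75 of 500). At a true 17% the figures are 0.259 and 0.128.

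**With a 50% fall at every baseline.** The highest qualifying value is half the baseline: 7.5% from 15%, 8% from 16%, 10% from 20%, 14.5% from 29%. The present text allows 15% in all four cases. In whole-number percentages the stricter rule never adds a PR, so the present wording can err only upward relative to it.

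**Scale.** One patient is 1/80 = 1.25 points of response rate at the maximum sample size.

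**Does PR count in ORR?** In Section 2.3, (7 + 1)/28 = 28.6%, given there as 28%, so the plan's own usage is CR plus PR. This describes an earlier study and does not define this trial's endpoint.

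**The case against.** The strongest reply is that a sensible assessor would apply the 6-15% range only to baselines of 15% or more. Then 10% to 10% is not a PR, and a reader who infers that most eligible disease categories meet the PR blast criterion before treatment goes too far. That stands: the inference needs the literal reading, which leaves the 50% clause nearly redundant. On the preferred reading, no fall at all is possible only at 15%, small falls suffice only just above it, and the 25-48% needed from 20-29% is not trivial.

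A reader might also infer that a PR need not reflect any response. The documents do not support that. Section 8.2 relaxes only the blast level, and the CR blood criteria still apply. What can be missing is a blast response. The count criteria do not close the gap entirely: they are levels rather than changes, Section 4.2.1 requires no cytopenia at entry, and Section 4.2.2 permits growth factors during the study.

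It is fair, too, that PR's place in ORR is inferred, and that no decision rule depends on it. Section 11.0 names overall survival as primary, Section 11.2 monitors CR and toxicity, and Section 11.3 plans interval estimates for CR rates only.

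Finally, Section 8.0 attributes the criteria to an international working group. That source cannot be consulted here, but Section 8 writes out its own definitions, and those are what assessors will apply. None of this answers the 16% to 15% case, which meets the blast part on either reading.

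**Conclusion.** The definition is faulty and should be corrected, but the defect is bounded. On the preferred reading it affects baselines of 15% and above, and is most marked at 15-19%, where a fall of 0-21% is enough against the 50% used elsewhere in Section 8. On the literal reading it extends to every baseline of 6-15%. The plan does not choose between the readings.

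How many patients would be misclassified cannot be derived, because the documents give neither the baseline blast distribution nor the share of patients who would meet the count criteria. The 1.25 points per patient is a scale, not an estimate of bias. The effect on ORR, response duration and relapse-free survival assumes that PR counts as response. The CR target of 20%, the CR and toxicity stopping rules, Tables 3-4 and the overall survival power and monitoring are unchanged.

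**What to change.** Replace the Section 8.2 definition with: *PR: all CR count criteria met, and marrow blasts decreased by at least 50% from pretreatment but still above 5%, at every baseline.* Drop the free-standing 6-15% range. This uses the threshold already in Sections 8.2 and 8.4 and leaves no gap below: from a baseline of 10% or less, a 50% fall reaches the CR blast level.

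Merely stating that the 6-15% range applies from 15% upward would remove the literal reading but leave 15% to 15% and 16% to 15% as qualifying.

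The cost is one sentence. Pretreatment marrow is already collected (Section 6.0), response marrows are already scheduled (Section 7.0), and no design figure changes. ORR may be slightly lower, and some high-baseline patients with a real but partial fall would no longer count: 20% to 12% is a fall of 8/20 = 40%.
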